## List of Abbreviations

AE	Adverse event
AUC	Area under the curve
BMI	Body mass index
CHS	Cardiovascular Health Study
CTRC	Clinical and Translational Research Center
CVD	Cardiovascular disease
ECG	Electrocardiogram
FDA	Food and Drug Administration
FT4	Free T4
HUP	Hospital of the University of Pennsylvania
IDS	Investigational Drug Service
IRB	Institutional review board
IV	Intravenous
LFTs	Liver function tests
LT3	Liothyronine
LT4	Levothyroxine
mRNA	Messenger ribonucleic acid
NHANES	National Health and Nutrition Examination Survey
NIA	National Institute on Aging
NIDDK	National Institute of Diabetes and Digestive and Kidney Diseases
NIH	National Institutes of Health
PHI	Protected health information
REE	Resting energy expenditure
SAE	Severe adverse event
SD	Standard deviation
SEM	Standard error of the mean
SF	Short form
T3	Triiodothyronine
T4	Thyroxine
TPO	Thyroid peroxidase
TRH	Thyrotropin releasing hormone
TSH	Thyroid stimulating hormone
TSH max	Maximum serum TSH concentration

CONFIDENTIAL

This material is the property of the University of Pennsylvania. Do not disclose or use except as authorized in writing by the study sponsor

## Study Summary

Title	The Thyroid Axis in Older Individuals with Persistent Subclinical Hypothyroidism: a Mechanistic, Randomized, Double-Blind, Cross-Over Study of Levothyroxine (LT4) and Liothyronine (LT3) Administration
Short Title	LT4 and LT3 in Subclinical Hypothyroidism
Protocol Number	821564
Phase	
Methodology	Randomized, Double-Blind, Cross-Over Study
Study Duration	Three years
Study Center(s)	Single-center
Objectives	To examine the pituitary-thyroid axis in older individuals with persistent subclinical hypothyroidism utilizing dynamic testing with thyrotropin releasing hormone (TRH) stimulation under different therapeutic conditions of either LT4 or LT3. We will measure thyroid stimulating hormone (TSH) area under the curve (AUC), $TSH_{max}$ , change in TSH bioactivity, and change in free T4 and total T3 levels. All outcomes will be assessed at baseline and after achieving target TSH levels with each thyroid preparation.
Number of Subjects	Thirty
Diagnosis and Main Inclusion Criteria	Men and women aged 70 and older with persistent subclinical hypothyroidism
Study Dose, Regimen	Product, Route, 1. Intravenous TRH 200 µg at study visit 1 (baseline), study visit 2 (on first thyroid treatment), and study visit 3 (on second thyroid treatment) 2. Oral LT4 with a total starting dose of 0.7mcg/kg/day split into three daily doses and titrated to a target TSH level of 0.5 -1.5mU/L 3. Oral LT3 with a starting dose of 1/3 of the weight based LT4 dose divided into three daily doses titrated to a target TSH level of 0.5 -1.5mU/L
Duration administration	of 1. Three single administrations of TRH (at baseline study visit 1, study visit 2 on the first thyroid treatment, and study visit 3 on the second thyroid treatment) 2. LT4 taken as divided doses three times daily 3. LT3 taken as divided doses three times daily 4. For LT4 and LT3, there will be medication adjustments every four weeks as needed until the TSH level is at goal.

CONFIDENTIAL

This material is the property of the University of Pennsylvania. Do not disclose or use except as authorized in writing by the study sponsor

Reference therapy	None
Statistical Methodology	Changes in TRH stimulation test parameters and other outcomes will be compared from baseline for each thyroid hormone preparation (LT4 or LT3) via paired t-tests and between treatment arms via two-tailed tests. AUC for TRH stimulated TSH response will be calculated. Nonparametric tests will be employed as needed.

CONFIDENTIAL

## 1 Introduction

This document is a protocol for a human research study. This study is to be conducted according to US and international standards of Good Clinical Practice (FDA Title 21 part 312 and International Conference on Harmonization guidelines), applicable government regulations, and Institutional research policies and procedures.

### 1.1 Background

Thyroid hormone is important for multiple physiologic functions, and insufficiency and excess of thyroid hormone are each pathologic conditions. Thyroid hormone is tightly regulated through a feedback loop between the hypothalamic hormone thyrotropin releasing hormone (TRH), the pituitary hormone thyroid stimulating hormone (TSH), and the thyroid hormones thyroxine (T4) and triiodothyronine (T3) (Fig. 1, from [1]). Individuals with normal thyroid function maintain TSH levels in a narrow range, though the setpoint for thyroid hormone levels varies between individuals.

[figure not shown]

Figure 1

With increasing age, there is a progressive shift toward higher TSH levels in people who have no detectable underlying thyroid disease

(Fig. 2, from [2]). This leads to a higher prevalence of subclinical hypothyroidism in older people. Subclinical hypothyroidism is defined as elevated TSH levels with normal levels of thyroid hormones. It is a common clinical diagnosis affecting 10-15% of individuals aged 65 years and older and up to 20% of those 85 years and older.[1-5] The purpose of this study is to examine mechanisms to explain the age-related increase in TSH levels and resulting subclinical hypothyroidism.

[figure not shown]

Figure 2

In addition, it is not clear if individuals with subclinical hypothyroidism benefit from replacement of thyroid hormone. Some argue that subclinical hypothyroidism should be treated as a form of mild hypothyroidism, whereas others argue that it may be adaptive. The question is whether, in older people, a TSH level just outside the reference range should be considered a pathologic finding. We hypothesize that slightly elevated TSH results from an age-related decrease in the function of TSH that leads to an adaptive shift in the pituitary-thyroid setpoint, rather than an early sign of thyroid failure. That is, the TSH that is produced by the pituitary gland may become less biologically active with older age. More TSH would then be required to keep thyroid hormone level production constant.

There is evidence to support the biologic plausibility of a decline in TSH bioactivity with age. TSH with decreased bioactivity has been detected using cell-based methodologies, and has been reported in conditions of thyroid axis dysfunction, ranging from primary and

CONFIDENTIAL

This material is the property of the University of Pennsylvania. Do not disclose or use except as authorized in writing by the study sponsor

secondary hypothyroidism to TSH-producing pituitary adenomas.[3-6] An inverse correlation between TSH bioactivity and age was also found in 11 healthy men and women aged 28-52 years.[4]

Changes in TSH structure including glycosylation patterns affect its biologic activity.[7] These changes in glycosylation could be due to alterations in TRH output from the hypothalamus, as is found with age for other hypothalamic hormones such as GHRH and GnRH. [8, 9] Unfortunately, TRH cannot be measured directly; however, TSH bioactivity can be measured before and after TRH stimulation testing to provide indirect evidence of this mechanism. We can then create perturbations to the system such as adding back thyroid hormones to understand these hormonal feedback loops. Together the TRH stimulation testing and the crossover design with T4 and T3 add back will provide insight into the dynamics of the hypothalamic-pituitary-thyroid axis in older people with subclinical hypothyroidism.

## ***1.2 Interventional Agents***

TRH, a naturally occurring hypothalamic neuropeptide in humans, is an endogenous ligand for the TRH receptor. It is composed of three amino acids and stimulates the release of TSH and prolactin from the anterior pituitary. The release of TSH then stimulates the release of thyroid hormones, T4 and T3 (Fig. 1). Synthetic TRH has been used for over 40 years in the diagnostic assessment of pituitary or hypothalamic dysfunction.

Intravenous TRH has a short half-life with a mean of approximately 5 minutes in normal subjects. Bassiri and Utiger administered 400 µg TRH to 8 healthy men and noted that plasma TRH levels rose from <0.4 ng/mL to  $33 \pm 7$  ng/mL (mean  $\pm$  SEM) 2 minutes after injection and linearly fell to 2.9 ng/mL 20 min after injection. The mean half-life of TRH was found to be  $5.3 \pm 0.5$  min.[10]. TSH levels rise rapidly; reach a peak, and later decline after TRH administration. Anderson *et al* administered 100-800 µg TRH to 79 healthy men and found that TRH-stimulated TSH levels peaked after 30 min and fell to baseline levels in approximately 3 hours.[11]

Levothyroxine (LT4) and liothyronine (LT3) are synthetic forms of T4 and T3, which are endogenous hormones produced by follicular cells of the thyroid gland in response to stimulation by TSH from the anterior pituitary. The majority of circulating thyroid hormone in the blood is in the form of T4. T4 is then converted to T3 in target tissues, with T3 being the more physiologically active hormone. Both T4 and T3 bind to the thyroid receptor in cell nuclei and regulate DNA transcription and protein synthesis. Human studies show that thyroid hormone levels can also alter TSH bioactivity. [4, 6, 12] T4 is metabolized slowly with eighty percent of circulating T3 derived from T4 through deiodination. The half-life of LT4 is six to eight days. The half-life of LT3 is one to two days.[13-15]

## ***1.3 Preclinical Data***

Slightly elevated TSH may result from an age-related alteration in the function of TRH, analogous to the age-related alterations found in other hypothalamic hormones such as

CONFIDENTIAL

This material is the property of the University of Pennsylvania. Do not disclose or use except as authorized in writing by the study sponsor

GHRH and GnRH.[8, 9] Preclinical data show that alterations to the structure and packaging of the TSH molecule may affect its function. TSH is a glycoprotein composed of an alpha and a beta subunit that requires glycosylation of three asparagine residues in order to have maximal function at the TSH receptor.[16] When the glycosylation pattern is abnormal, TSH binding to its receptor is less efficient, resulting in decreased bioactivity. These changes in glycosylation could be due to alterations in TRH output from the hypothalamus, as suggested by animal models.[7, 17-19] Taylor et al. showed that hypothalamic as compared to primary hypothyroidism caused by lesions in the rat paraventricular nuclei alters carbohydrate structure of secreted thyrotropin. Taylor and Weintraub later showed that this alteration in TSH carbohydrate structure could be corrected by administering TRH *in vivo*.[19] Hypothalamic TRH output cannot be measured directly. However, TSH bioactivity can be measured before and after TRH stimulation testing to provide indirect evidence of this mechanism.

In addition to TRH, there is evidence that thyroid hormones themselves can alter the bioactivity of thyroid stimulating hormone. Thyroid hormone status has been shown to modulate glycosyltransferase mRNA levels in mouse thyrotrophs.[20] This has been postulated to result from a direct action of T3 on thyroid hormone responsive elements in the upstream regulatory region of the sialyltransferase gene. If so, TSH glycosylation could be affected by the observed age-associated decline in T3 levels.

Rodent data indicate that replacement therapy with LT4 alone does not achieve adequate levels of T3 in all tissues.[21] However, combined replacement therapy of LT3 to LT4 completely restored euthyroidism in thyroidectomized rats at much lower doses of LT4 than those needed to normalize LT3 in most tissues when L-T4 alone was used. The LT4-LT3 cross-over design will give us insight into this mechanism.

#### **1.4 Clinical Data to Date**

In men and women from the Cardiovascular Health Study with a mean age of 74 years at the time of the initial TSH, we found a gradual increase in TSH levels over a 13-year period, with an average increase of 0.28 mU/L ( $p<0.01$ ) and no change in free T4 levels, suggesting a shift in the pituitary-thyroid setpoint. These data parallel the 0.32 mU/L TSH increase over a 13-year period published in a younger population (mean age 58 years at the second TSH), also without change in free T4 levels.[22] NHANES data also illustrate a progressive shift toward higher TSH levels with increasing age [2] and another study has shown higher TSH in people with exceptional longevity.[23]

The hypotheses that there is a decline in TSH bioactivity with age and that thyroid hormone supplementation can alter bioactivity are supported by data in humans [4, 6, 12]. Oliveira et al. evaluated *in vitro* serum TSH bioactivity and found a strong inverse correlation between serum TSH bioactivity and age in 11 normal controls. This study also showed a decrease in TSH bioactivity in patients with primary hypothyroidism. The bioactivity improved with levothyroxine supplementation and was positively correlated with change in T3 levels but not free T4 levels. Evaluation of TSH glycosylation patterns showed a higher proportion of sialylated TSH molecules in patients with decreased

CONFIDENTIAL

This material is the property of the University of Pennsylvania. Do not disclose or use except as authorized in writing by the study sponsor

bioactivity, which decreased after LT4 replacement.[4] Increase in sialylation of the TSH molecule was also shown in patients with central hypothyroidism due to Sheehan's syndrome [3] and chronic TRH administration in patients with central hypothyroidism has been shown to improve TSH bioactivity.[24] These data suggest that hypothalamus-pituitary-thyroid feedback loops are regulated by TSH bioactivity and thyroid hormone levels.

### **1.5 Dose Rationale and Risk/Benefits**

#### **TRH stimulation testing:**

TRH has a short half-life and does not exhibit a sustained biological effect after a single intravenous bolus. For decades, TRH has been intravenously administered to a variety of study populations, including patients with thyroid, pituitary, and hypothalamic disorders.[10, 11, 25] In this study we will be using the standard clinical dose of 200 µg at three time points. This dose has been used in studies of dynamic pituitary testing utilizing TRH stimulation testing.[25, 26] Side effects have been reported in about 50% of patients, but side effects are generally minor and persist for only a few minutes following injection.

These side effects include[27]:

Most frequent: transient nausea, flushing, palpitations (without change in heart rate), lightheadedness, bad taste in mouth, abdominal discomfort, dry mouth, and an urge to urinate

Less frequent: anxiety, sweating, tightness in throat (without change in oxygenation or respiration), pressure in chest, tingling sensation, and drowsiness

Uncommon: change in blood pressure, seizure

The mean elevation of blood pressure reported was 16 mm of mercury. The peak blood pressure elevation occurred between one and five minutes, with a return to baseline blood pressure levels within ten minutes.[11] Participants with uncontrolled blood pressure or history of ischemic cardiac disease or stroke will be excluded.

Seizures have only been reported in those with a history of seizure disorder. Individuals with a history of seizure will be excluded.

No direct benefits are expected to result from TRH administration.

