### **3.4 Primary Safety Endpoints**

Participants will undergo ECG testing at the screening visit so that a baseline EKG is on file. Hyperthyroid symptoms will be assessed to monitor participant safety. Symptoms of palpitations and shortness of breath will be assessed every two weeks by telephone while

CONFIDENTIAL

This material is the property of the University of Pennsylvania. Do not disclose or use except as authorized in writing by the study sponsor

the participant is on study drug. See Appendix 1 for the hyperthyroid symptom lists for phone contacts and study visits.

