### 4.2 Exclusion Criteria

Laboratory Tests:

1. thyroid peroxidase (TPO) antibody positive
3. abnormal liver function tests (LFTs >3 x upper limit of normal)
4. hemoglobin <11 g/dL

Surgeries or Procedures:

1. thyroid surgery
2. pituitary surgery
3. bariatric surgery
4. Bowel resection involving the jejunum and upper ileum
5. radioactive iodine therapy
6. radiation treatments to head or neck

Medical Conditions:

1. diagnosis of pituitary disease
2. diagnosis of amyloidosis, sarcoidosis, hemochromatosis
3. diagnosis of adrenal insufficiency
4. obesity with BMI > 35 mg/kg
5. history of stroke
6. chronic or ongoing angina, Class II or higher congestive heart failure, or uncontrolled hypertension with current blood pressure greater than 160/100
7. diabetes mellitus with hemoglobin A1C level greater than 8.0% in the past six months
8. celiac sprue, Crohn's disease, ulcerative colitis, Zollinger-Ellison syndrome
9. renal insufficiency with calculated glomerular filtration rate <45 cc/min
10. cognitive impairment with Mini Mental State Exam[36] <24/30
11. history of any seizures
12. unstable medical or psychological condition in the judgment of the principal investigator

Medications:

1. thyroid hormone preparations
2. antithyroid drugs
3. medications that interfere with the absorption or metabolism of thyroid hormone

CONFIDENTIAL

This material is the property of the University of Pennsylvania. Do not disclose or use except as authorized in writing by the study sponsor

4. medications that interfere with the TRH stimulation test
5. proton pump inhibitors

Please see Appendix 3 for full list of medications

Exogenous estrogen and testosterone is not an exclusion, but all participants will be required to remain on the same dose throughout the study.

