### **5.6 *Prior and Concomitant Therapy***

Prior and concomitant medication history will be collected for each subject. Medications that are used on a daily basis, and are used to treat medical conditions that do not meet exclusion criteria will be permitted. Excluded prescription medications include thyroid hormone preparations, antithyroid drugs, corticosteroids, medication that interferes with the TRH stimulation test, and medication that interferes with the absorption or metabolism of LT4 or LT3 (Appendix 3).

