## **6.2 Visit 1 (Day 1)**

Participants will arrive at 7:30 am after a 12-hour fast. Weight and vital signs including heart rate, rectal temperature, and blood pressure will be measured. The activity and heart rate monitors will be collected. An REE evaluation by indirect calorimetry will be completed.

An IV will be inserted into the forearm and blood will be collected at times -5 and 0, followed by injection of 200 µg TRH.[28] Additional blood will be collected at 5, 10, 15, 20, 30, 60, 120, and 180 minutes, immediately processed, and stored at -80 degrees for measures of TSH, free T4, and total T3 (all time points), prolactin, alpha subunit, reverse T3 (0, 60, and 180 minutes), and a lipid profile (time 0). Additional samples at the 0, 120, and 180 time points will be processed and saved for TSH bioactivity measurements and TSH structure evaluation. If the participant consents to the optional exploratory genetic research study, then a sample will be collected, processed and saved for genetic testing at one study visit only (time -5).

Blood pressure will be monitored before administration of TRH, and at 5, 15, 30, 60, 120, 180 minutes.

Questions about health status, quality of life, and hypothyroid symptoms will be completed. Digit symbol substitution test will be completed.

Participants will be provided with lunch and undergo a DXA scan.

Participants will then undergo arterial tonometry and Doppler echocardiography testing. Assessment of arterial load will be made from this data.

Arterial tonometry: We will use a commercially available system (SphygmoCor, AtCor Medical) that uses a high-fidelity applanation tonometer (Millar Instruments; Houston, TX). The tonometer will be used to record carotid, radial and femoral arterial pressure waveforms. Mean brachial pressure will be obtained from a radial waveform calibrated with brachial systolic and diastolic pressures, measured with a validated oscillometric device. Diastolic and mean pressures will then be used to calibrate the carotid pressure waveform. Carotid-femoral and carotid-radial pulse wave velocity (PWV) will be computed from the time delay between the waveform foot on these arterial sites and the distance between the sites (measured on the body surface), where PWV = distance/time.

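### Section 1.5 rules out past ischemic heart disease because of TRH risk, but the Section 4.2 list excludes only chronic or ongoing angina

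*Combined protocol and SAP*

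**What the plan says.** Section 1.5, under TRH stimulation testing, describes the effect on blood pressure: "The mean elevation of blood pressure reported was 16 mm of mercury". It places the peak between one and five minutes after injection and the return to baseline within ten minutes. It then says: "Participants with uncontrolled blood pressure or history of ischemic cardiac disease or stroke will be excluded". A separate statement excludes anyone with a past seizure. The same section adds: "No direct benefits are expected to result from TRH administration".

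Section 4.2 is the list that screening staff would apply. Its Medical Conditions part includes past stroke (item 5) and any past seizure (item 11). Item 6 reads: "chronic or ongoing angina, Class II or higher congestive heart failure, or uncontrolled hypertension with current blood pressure greater than 160/100". The only catch-all is item 12: "unstable medical or psychological condition in the judgment of the principal investigator".

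On the screening ECG, Section 3.4 says: "Participants will undergo ECG testing at the screening visit so that a baseline EKG is on file". On monitoring during the TRH test, Section 6.2 says: "Blood pressure will be monitored before administration of TRH, and at 5, 15, 30, 60, 120, 180 minutes".

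**The concern.** Section 1.5 tells an ethics board or safety reviewer that people with past ischemic heart disease will not receive TRH. Section 4.2 does not apply that rule, because it replaces past disease with current angina. Someone whose ischemic disease is in the past and now free of angina falls between the two.

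The population makes this a realistic case. Participants are 70 or older and are recruited from general medicine, geriatrics and endocrine clinics. Each has a TRH injection at Visits 1, 2 and 3. Because no direct benefit from TRH is expected, risk control depends heavily on who is let in. Section 1.5 also lists palpitations and a feeling of pressure in the chest among the known side effects, and these would be harder to interpret in someone with past ischemic disease.

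**Working it through.** No formula settles this point. The check is to set the exclusions promised in 1.5 against the items in 4.2.

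| Condition excluded in 1.5 | Item in 4.2 Medical Conditions | Match? |
|---|---|---|
| Uncontrolled blood pressure | Item 6, made specific as above 160/100 | Yes |
| Stroke | Item 5, past stroke | Yes |
| Past seizure | Item 11, any past seizure | Yes |
| Past ischemic cardiac disease | Item 6, chronic or ongoing angina only | No, narrowed |

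Four conditions are named, three carry over, and one is narrowed.

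**Test case.** Consider a person with a prior myocardial infarction or coronary revascularization (my examples; the documents name neither), no chronic or ongoing angina, no heart failure of Class II or above, blood pressure not above 160/100 and a stable condition.

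- Items 5 and 11 do not apply.
- Item 6 does not apply, because none of its three parts is met.
- Item 12 does not apply, because it reaches only unstable conditions.
- The ECG does not exclude the person. Section 3.4 gives its purpose as a baseline record, and no ECG finding is an eligibility criterion.

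So 4.2 admits a person whom 1.5 excludes.

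**Could text have been lost?** The Laboratory Tests list in 4.2 has a numbering gap (no item 2), but Medical Conditions runs from 1 to 12 without a break. Missing text does not explain the difference.

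**Exposure.** 3 visits × 1 injection = 3 injections, and 3 × 200 µg = 600 µg of TRH in total per participant.

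**Monitoring.** The first blood pressure reading after TRH is at 5 minutes, the end of the stated one-to-five-minute peak window, so monitoring does not stand in for the exclusion.

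**Illustration only.** If the 16 mm of mercury mean rise is systolic (an assumption; 1.5 does not say), a participant at the permitted limit would average 160 + 16 = 176 mm of mercury at the peak. This holds with or without ischemic disease, so it gives the setting and does not measure the gap.

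**The case against.** The strongest reply is that the exclusion is stated. Section 1.5 is current protocol text, so enrolling such a person would breach the protocol. On that view the defect is an incomplete list. This is fair as far as it goes, and the harm does depend on staff working from 4.2 alone. But 4.2 is where staff look. Section 10.1 has the inclusion and exclusion criteria fully source-verified, and a check against 4.2 would find the enrolment compliant.

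A second reply is that 1.5 is a summary and item 6 makes it operational, just as it turns uncontrolled blood pressure into a threshold. The wording counts against this. Items 5 and 11 refer to history where past disease is meant, and the angina wording in item 6 does not. Still, the documents cannot show which of the two texts is the mistake, so the fix must allow for either.

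Third, the blood pressure evidence is limited. The 16 mm figure is cited to a study that Section 1.2 describes as 100–800 µg TRH in 79 healthy men, whereas this trial gives 200 µg to people of 70 and over. Section 1.5 also lists blood pressure change among the uncommon effects, and it does not say outright that the blood pressure rise is the reason for the ischemic exclusion. That link is inferred from the order of the sentences. These points rightly keep the 176 mm figure as an illustration.

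Fourth, there are real safeguards. The rise is brief, and TRH is given supine by a nurse. Screening includes a thorough history and a physical examination, withdrawal for unacceptable risk is allowed (4.4.1), and an external medical monitor is in place. Past disease would probably be known, and harm is less likely as a result. None of these supplies a rule to exclude on it.

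**Conclusion.** The concern holds. Sections 1.5 and 4.2 disagree on ischemic cardiac disease, and 4.2 as written admits people whom the TRH risk statement says are excluded. The text mismatch is certain; the size of the consequence is not. The number of people affected is unknown. For each one, the exposure is three 200 µg TRH injections outside the protocol's own risk rationale. The conclusion assumes only that eligibility is decided from 4.2; it does not depend on the 16 mm figure or on its being systolic. Endpoints, sample size and power are not affected. The inconsistency should be corrected, but it does not undermine the trial's analysis.

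**What to change.** Add one item to the 4.2 Medical Conditions list: past ischemic cardiac disease, including prior myocardial infarction or coronary revascularization. If the investigator and IRB intend to admit people with past disease and no current angina, correct the risk statement in 1.5 instead and give the safety justification. Either way it is a one-line amendment. The first option may make a few screened people ineligible.

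A separate wording point can go into the same amendment. Section 5.6 says "Excluded prescription medications include thyroid hormone preparations, antithyroid drugs, corticosteroids", but neither the 4.2 medication list nor Appendix 3 names corticosteroids. They should be added to both.
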